**AIM 1: Examine whether conventional cigarette smokers can significantly reduce their combustible cigarette use by switching to SREC.** We hypothesize that smokers randomized to the flavor choice condition will show significantly greater reductions in combustible cigarette use than smokers in the usual flavor condition. We will assess changes in use of products over a 12-week trial. We will also examine moderators of effects, including sex, baseline menthol cigarette use (not SREC flavor), and nicotine dependence level at baseline.

**AIM 2: Examine whether reductions in conventional cigarette use and uptake of SREC are associated with changes in health and biomarker variables.** We will have longitudinal measures of all

combustible tobacco products as well as SREC use and will examine how these longitudinal changes in patterns of use are associated with changes in expired air carbon monoxide (CO); blood pressure; heart rate; weight; respiratory symptoms; withdrawal symptoms; and nicotine dependence. We hypothesize that smokers who show more complete substitution will show greater reductions in CO and respiratory symptoms.

**AIM 3: Examine smokers' subjective responses to SREC in real time, as they are used, and whether these responses are associated with cigarette reduction.** We hypothesize that smokers in the flavor choice condition will show more adherence to the switching intervention and report higher levels of satisfaction, pleasure, and mood enhancements than smokers in the usual flavor EC condition and that these responses will predict level of cigarette reduction. Data will come from EMA measures and daily surveys. We will also descriptively examine how SREC flavor may be associated with subjective responses.

**AIM 4: Examine how patterns of use (e.g., contexts, timing) and subjective experience with SREC differ from conventional cigarette use, and whether differences are associated with success in switching to SREC.** These within-subject analyses will use EMA data. We hypothesize that subjects who have fewer differences in patterns and experiences between cigarettes and SREC will reduce cigarettes more and maintain SREC use longer.

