**Aim 3: Examine smokers' subjective responses to SREC in real time, and whether these responses are associated with cigarette reduction.** Levels of satisfaction, pleasure, mood change following use, and withdrawal symptoms will be assessed via EMA during the second week of SREC use. Level of satisfaction, pleasure, and mood will be assessed following each use of SREC (event report), and withdrawal symptoms will be assessed both during random times and following SREC use. We will also descriptively examine how the SREC flavor may be associated with adherence and overall level of subjective responses. We will use linear mixed models to compare groups in terms of the EMA subjective reports and withdrawal symptoms. Also, using the empirical Bayes estimates from these linear mixed models of EMA-reported subjective experience and withdrawal, we will examine whether these predict longitudinal changes in cigarette use over the following weeks, which will be modeled using a Poisson mixed model including effects of group, time (and group by time if significant). We will specifically examine the effects of satisfaction and withdrawal on cigarette use, both as main effects and as interactions with time if significant. Again, we will follow the resampling approach to account for the uncertainty of the empirical Bayes estimates.

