**Aim 4. Examine how patterns of use (e.g., contexts, timing) and subjective experience with SREC, differ from conventional cigarette use, and whether differences are associated with success in switching to SREC (giving up or reducing combustible and using SREC).** We will have baseline EMA data on smoking events and random time sampling of urges, mood, satisfaction with smoking, as well as context. Then we will have a week of EMA data on the second week of the instructed switch to SREC. We will compare EMA data during baseline to the SREC switch week on the following within subject factors: context of use (alone, with others; location – home; work; in public; presence of other smokers; time of day (e.g., first cigarette of the day); mood prior to use; mood after use; urge prior to use and at random time; satisfaction after use). We will use three-level (observations within weeks within subjects) linear mixed models for continuous outcomes (mood), logistic mixed models for binary outcomes (context), and survival mixed models for time to an event (first cigarette of the day). The main independent variable will be the indicator of EMA week (baseline/switch week) to test whether the outcomes vary by EMA week. We will also control for group (usual flavor/flavor choice) and examine whether the effect of EMA week varies by group. Analyses will also include sex and prior menthol use as covariates.

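### Aim 4 hypothesises that smaller cigarette–SREC differences go with more cigarette reduction and longer SREC use, but neither of those outcomes enters any model specified for the aim

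*Combined protocol and SAP*

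**What the plan says.** Section 3.0 gives Aim 4 two parts: how patterns and experience differ between SREC and cigarettes, and whether those differences relate to switching success. The hypothesis belongs to the second part: "subjects who have fewer differences in patterns and experiences between cigarettes and SREC will reduce cigarettes more and maintain SREC use longer". The Aim 4 heading in section 9.0 repeats the intent, "whether differences are associated with success in switching to SREC (giving up or reducing combustible and using SREC").

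The method text under that heading starts from a comparison of the two EMA weeks: "We will compare EMA data during baseline to the SREC switch week on the following within subject factors". The factors listed are context of use, time of day, mood before and after use, urge and satisfaction. The models are three-level linear, logistic and survival mixed models. On predictors it says "The main independent variable will be the indicator of EMA week (baseline/switch week) to test whether the outcomes vary by EMA week", then "We will also control for group (usual flavor/flavor choice) and examine whether the effect of EMA week varies by group" and "Analyses will also include sex and prior menthol use as covariates". The Aim 4 text ends there.

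Section 12.0 powers Aim 4 with 108 subjects, 20 smoking and 10 SREC events each, and an ICC of 0.3 to 0.4. It gives a detectable odds ratio of 1.25 at power 0.8 on a two-sided 0.05 test, and describes this as excellent power for within-subject cigarette-versus-SREC comparisons.

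**The concern.** The hypothesis ranks people: those whose SREC use most resembles their smoking should switch best. Testing it needs one quantity per person for the cigarette–SREC difference and an outcome for later switching. The specified models supply neither. They estimate whether the average report shifts between two weeks, and whether that shift differs between flavor arms.

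These questions can have different answers. An average shift can exist with no link to switching success. A link can exist with no average shift, if individual shifts run in both directions. If nothing is added, the difference measure, the factors, the switching outcome and the model would all be chosen after the data are seen, from a list of at least half a dozen EMA factors. A numbered hypothesis would then rest on an analysis that was not planned.

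**Working it through.** **1. The hypothesis and the models side by side (sections 3.0 and 9.0).**

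| Needed by the hypothesis | In the Aim 4 models |
|---|---|
| Outcome: cigarette reduction | Absent |
| Outcome: duration of SREC use | Absent, and not defined |
| Predictor: each person's cigarette–SREC difference | Absent; the predictors are EMA week, group, week-by-group, sex and prior menthol use |

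The three-level structure (observations within weeks within subjects) would allow person-specific week shifts to be estimated, but no step carries them forward.

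**2. The neighbouring aims.** Aim 2 puts empirical Bayes estimates of change in use into second-stage models, with resampling for their uncertainty. Aim 3 does the same with EMA estimates: "we will examine whether these predict longitudinal changes in cigarette use over the following weeks, which will be modeled using a Poisson mixed model". Its predictors are levels of SREC subjective experience and withdrawal, and its outcome is cigarette use. No aim has the cigarette–SREC difference as a predictor or SREC maintenance as an outcome.

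**3. Week is not product.** Section 12.0 allows both products in the switch week. Take an event-level report and let D be a subject's SREC-minus-cigarette difference, assuming that cigarette reports themselves do not change between weeks. The week shift is then s × D, where s is the SREC share of switch-week events. With the plan's 20 smoking and 10 SREC events, s = 10/30 = 1/3, so the shift is D/3. A subject whose events were all SREC would show D. The week shift therefore depends on how far the person has already switched, as well as on how different the products feel.

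**4. The power statements.**

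*Aim 4.* I used a random-intercept logistic model with variance ICC/(1−ICC) × π²/3, which is 1.41 at ICC 0.3 and 2.19 at ICC 0.4. Information is I = 108 × E[w₁w₂/(w₁+w₂)], with w₁ = 20p₁(1−p₁) and w₂ = 10p₂(1−p₂). Power is Φ(ln 1.25 × √I − 1.96).
- Odds ratio read as subject-specific, base proportion 0.3 to 0.5 (assumed): 0.73 to 0.75 at ICC 0.3, and 0.69 to 0.71 at ICC 0.4. Simulation at base proportion 0.5 gives 0.73 and 0.72.
- Odds ratio read as population-averaged, base proportion 0.2 to 0.5: 0.79 to 0.94.

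The stated 0.8 lies between the two readings. It can be neither confirmed nor refuted, because the base proportion and the odds-ratio scale are not given.

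*Aim 2.* This is the plan's only power figure for a correlation across subjects: r = .262, n = 108. Fisher z gives Φ(0.268 × √105 − 1.96) = Φ(0.79) = 0.785, and the noncentral t gives 0.798. It reproduces, but it is stated for SREC usage and health outcomes.

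No figure is given for Aim 4's association.

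**5. Illustration on assumed inputs.** 108 subjects; true difference normal with SD 1 and mean μ; switching success correlated −ρ with the absolute difference; observed difference measured with a stated reliability. A one-sample t-test on the mean difference stands in for the week test. The three-level event models were not simulated.

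| μ | ρ | Reliability | Mean-shift test rejects | Test on absolute difference rejects |
|---|---|---|---|---|
| 0.3 | 0 | 0.8 | about 78% | about 5% |
| 0.5 | 0 | 0.8 | over 99% | about 5% |
| 0 | 0.4 | 0.8 | about 5% | about 90% |
| 0 | 0.4 | 0.6 | about 5% | about 65% |
| 0 | 0.4 | 0.4 | about 5% | about 34% |

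At ρ = 0.262 the second-stage test has about 56% power at reliability 0.8 and about 32% at 0.6. If success instead follows the signed difference (ρ 0.4, zero mean, reliability 0.8), a test on the absolute difference has about 8% power and a signed test about 97%. The form of the difference therefore has to be chosen in advance.

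**The case against.** The strongest reply is that this is an unstated model rather than a wrong one. A week comparison is reasonable for the first half of the aim, the heading still names the association, and nowhere does the plan say that the week test decides the hypothesis. That stands. A reader might infer that the sponsor intends a significant week effect as proof of the hypothesis. The documents do not say so, and with many EMA outcomes there is no single Aim 4 p-value.

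It is also fair that the analysis covers more than a two-week comparison. It includes the week-by-group term, and section 12.0 adds cigarette-versus-SREC contrasts and comparisons with random prompts. None of these involves reduction or SREC maintenance. Aim 3 narrows the gap by linking EMA levels to later cigarette use, but it does not close it.

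The simulation shows something true by construction, and its shifts, correlations and reliabilities are not in the documents. Treating r = .262 as an Aim 4 assumption would be wrong, since it is Aim 2's detectable correlation. The argument does not need these figures.

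Brevity is a weaker defence: the same section spells out the linking step for Aims 2 and 3 and stops before it for Aim 4.

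**Conclusion.** The point holds for the second half of Aim 4. As specified, the analysis describes how EMA reports change between weeks and whether that change differs by arm. It leaves the aim's hypothesis untested. The conclusion follows from the model terms alone and rests on no numerical assumption. Its size cannot be given as a figure for this trial, so the simulated rejection rates are illustrative only.

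Two further inferences should be resisted. The Aim 4 power of 0.8 is not shown to be wrong; it answers a different question. The primary endpoint, the Aim 1 group difference in cigarettes at the 12-week timepoint, is unaffected, as are sample size and data collection. This should be corrected before analysis, but it does not threaten the trial's main conclusion.

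**What to change.** Keep the EMA-week models and label them as the descriptive part of Aim 4. Add a second stage on the pattern of Aims 2 and 3:

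- Estimate each subject's cigarette-versus-SREC difference by product used, not by week alone.
- Do this for a small set of factors named in advance, and fix for each whether the difference is absolute or signed.
- Enter the estimates, with the same resampling for their uncertainty, in the mixed count models for cigarettes per day and for SREC use in the weeks after EMA wave 2, with group and time.
- Define an SREC-maintenance outcome in advance and model it on the same estimates.
- State how subjects with no SREC events in wave 2 are handled, since they have no SREC reports from which to form a difference.
- Base the Aim 4 association conclusion on these coefficients, and do not extend the section 12.0 power claim to it.

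No new data are needed: the EMA waves, daily use reports and returned pod weights are already planned. The cost is plan wording and about three models per factor (cigarettes, SREC use, maintenance), so three factors would mean nine. Power will be lower than for the within-subject contrast. Any figure quoted for it should state its assumed correlation and reliability.

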## 10.0 Quality Control and Quality Assurance

A detailed and robust quality assurance plan is essential for ensuring the scientific rigor and management of any study. Using our study protocol, good clinical practice, and documented standard

operating procedures, we will have written materials to support all study procedures. We will establish clear study roles and responsibilities that will promote dialogue across staff and ensure proper study execution across roles, with checks built into the overall quality plan at many points. We will provide training materials and procedures and demo versions of key software products or devices (EMA phones) with cases mocked to real-world scenarios to train staff before encountering actual participants. All clinical staff will conduct mock visits with EMA interviews and behavioral counseling under supervisor observation to ensure competence with following study procedures before permitted to operate independently. [name] will also observe 10% of each clinical staff treatment sessions in order to ensure the intervention is delivered appropriately. We have several years of senior staff experience with our two-stage screenings process that involves potential participants first completing an online screener, followed by staff phone call completion of a second screener. We have existing REDCap screening and scheduling databases running similar models. For our various data collection instruments, we will have scheduled reviews of collected data as well as random checks. Our quality procedures will involve automated programming/statistical checks executed at the time of individual data collection as well as report listings and aggregate statistics on groups of cases. The Data Manager, [name] conducts checks weekly or monthly, depending on the data being reviewed. If cleaning edits are appropriate for the quality of the data, all edits will maintain an audit trail of original and final value, reason for edit, date of change, and name of person making the change. Lastly, we will require that coded syntax be used by all data management and analytical staff for any data formatting, editing, and all analysis. All analyses must be reproducible programmatically.

## **11.0 Data and Safety Monitoring**

This trial will be monitored by [name]. (PI), [name]. (Co-I), [name] (Data Manager), and an independent Data Safety Monitoring Board (DSMB) that will be chaired by a medical safety monitor: [name], MPH, FAAP, Professor of Pediatrics, College of Medicine, UIC. The DSMB will meet at the start of the trial to review the study protocol, safety and ethical issues, and to approve plans for data integrity. [name], [name], and [name] will meet weekly during the data collection phase to review and monitor the following items: participant accrual, participant complaints, participant drop-out, reasons for drop-out, adverse events, and any other problems related to study participation. Data accuracy and completeness will also be monitored weekly. During active recruitment, the DSMB will join these data review meetings quarterly to monitor participant safety.

The data report will be updated on a weekly basis and will include: participant accrual, participant complaints, participant drop-out, reasons for drop-out, adverse events, and any other problems related to study participation. The report will also include preliminary data on cigarette and SREC usage on a participant basis.

An AE is defined as any untoward medical or psychological event experienced by a patient during or as a result of his/her participation in the study that represents a new symptom or an exacerbation of an existing condition whether or not considered study-related based on appropriate medical judgment. SAEs are any adverse experience that results in any of the following outcomes: death, life-threatening event/illness, inpatient hospitalization or prolongation of existing hospitalization, persistent or significant disability/incapacity, pregnancy resulting in a congenital anomaly/birth defect, or any event requiring medical or surgical intervention to prevent permanent impairment or damage. In this study, this is defined as physician confirmed diagnosis of any of the following: angina pectoris, heart attack, stroke, transient ischemic attack, heart failure, coronary angioplasty or bypass surgery, peripheral vascular disease, and cancer (except for non-melanoma skin cancer). Non-SAEs are all adverse events that do not meet the above criteria for "serious."

AEs will be systematically identified by querying participants at each of the in-person data collection time points after the start of treatment (week 2) through end of treatment (i.e., at weeks 3, 4, 6, 8, 11, and 14) using a standardized AE Patient Query Form to be adapted from [name] prior research studies using NRT while reducing cigarettes. AEs discovered outside of those planned evaluations, such as through other administrative interactions between research staff and participants (e.g., appointment reminder or rescheduling calls), will also be documented using the standardized AE form and followed up with to assure participant safety. Research staff will complete the AE forms directly into a centralized REDCap database in these circumstances. [name] will receive an automatic notification from REDCap upon submission of every AE report in order to trigger a review. The study safety monitor ([name]) will review, adjudicate, and document decisions or request that additional details be gathered from the participant, all

within the secure UIC REDCap web portal. Using this system, real-time AE reports can be generated at any time for the DSMB, UIC IRB, and/or NIDA, for both regularly scheduled reviews as well as in the event of any SAEs requiring expedited reviews.

**Expedited reporting.** All unexpected SAEs will be reported to the DSMB within 5 business days of discovery, regardless of any judgment of their relatedness to the study treatment. This reporting timeframe is consistent with the UIC IRB's requirements as described below. All relevant information will be reported to the DSMB for each unexpected AE including information about the event and its outcome, dosing history of a suspect medication/treatment, concomitant medications, the participant's medical history and current conditions, and all relevant laboratory data. An initial notification with all related study forms shall be made to the DSMB within 72 hours of the detection of an unexpected SAE. Any additional information about the case that may be obtained after the initial notification shall be communicated to the DSMB in a timely manner. The DSMB may require a conference call to review all the relevant information and the study safety monitor's determination of whether there was any possible relevance to the study and discuss and approve a Corrective and Preventive Action Plan, if warranted.

**IRB requirements for AE reporting.** The UIC IRB requires that within 5 business days of the PI learning of an unanticipated AE or major protocol deviation, the PI inform the Director of IRB panel and all relevant oversight committees at the university. Within 15 business days of the PI becoming aware of non-SAE, changes in risk/benefit, or events requiring report to the sponsor, these will be reported. This timeline satisfies the NIDA reporting requirements for AEs and unanticipated problems. An annual report will be submitted to the IRB and to the sponsor summarizing all AEs, serious or not.

**Reporting Mechanisms of IRB actions to NIDA.** The study PI will notify NIDA, through our Program Officer, within 5 days should our IRB put an administrative hold on the project or if the IRB issues a suspension or termination of IRB approval for the study.

**Reporting SREC Adverse Experiences to FDA.** In our ADVICE/INFORMATION letter from the Center for Tobacco Products at the FDA, they encouraged us to report adverse experiences with the SREC through the CTP Safety Reporting Portal Pathway for Researchers. We plan to follow the same timeline for reporting these events as described above for reporting to IRB and NIDA.

**Management of SAEs or Other Study Risks.** We believe that the risks of SREC are minimal, given the prevalence of use of e-cigarettes and the consensus that they are far less harmful than conventional cigarettes. SAEs will be immediately reported to the medical monitor, [name] and to the IRB. [name] will address these with the participant to ensure that the participant is linked with appropriate follow-up medical care.

We will discuss potential risks with participants at study enrollment and consent. We will discuss with participants that all tobacco use may present some harm, and that no tobacco use is healthy. We will also provide education to participants on the symptoms of nicotine toxicity (nausea and vomiting) so that they are aware and can reduce their exposure if they experience these symptoms. We also will provide participants with education on the recent outbreak of EVALI cases and how to identify if they may be experiencing the early signs and symptoms of an EVALI. At the enrollment visit (during the consent process) and at the end-of-treatment visit, we will tell participants that the long-term safety and health effects of using e-cigarettes is unknown. We will also discuss in-person and include on the information sheet that the SREC device may contain nicotine which can be hazardous to children and pets if ingested, in addition to informing the risk of nicotine use for pregnant and/or nursing women. We plan to discuss the safe and secure storage of the device and pods in their homes. Additionally, we will clearly label the SREC packaging so that participants are aware the SREC is used "for investigational purposes only."

Clinical study staff are the first line of staff to monitor and assess AEs and UPs. These will be assessed at each study visit after week 2. They will be recorded in REDCap responses to short surveys and in written responses to interview questions. Staff will notify [name] about these events during weekly supervision, but [name] will also receive emails as Adverse Event Reports are submitted to the REDCap database. Plans will be developed to manage and monitor AEs and UPs. SAEs will be immediately reported to the medical monitor, [name]. [name] will address these with the participant to ensure that the participant is linked with appropriate follow-up medical care. In our REDCap database, we will have a programmed report for AEs and UPs that can be run as needed for review to ensure that our understanding of adverse events and problems is always up to date.

**Trial Stopping Rules.** This is a low-risk trial and will be conducted over a short time span. Thus, we do not have any formal stopping rules for safety. If at any time during the course of the study, the DSMB judges that the risk to participants significantly outweighs the potential benefits (which is unlikely given the evidence base for the proposed interventions), the DSMB shall have the discretion and responsibility to request all necessary information for detailed analyses, and if warranted, recommend that the study be terminated. Stopping rules for the trial could include stopping because of a significant number of injuries or illnesses that can reasonably be attributed to participation in the study, inability to recruit and measure the required number of participants to conduct the primary outcome analyses, poor intervention quality and delivery, serious deviation from study protocols, or other circumstances that would render the study unlikely to produce scientifically valid findings. The DSMB will carefully weigh the risk of completing the trial as planned against the risk of prematurely stopping the trial for safety or futility.

If participants drop out before the end of the study, we will make every effort to collect their SREC device and all used and unused pods that have been distributed.

**Expedited reporting.** All unexpected SAEs will be reported to the DSMB within 5 business days of discovery, regardless of any judgment of their relatedness to the study treatment. This reporting timeframe is consistent with the UIC IRB's requirements as described below. All relevant information will be reported to the DSMB for each unexpected SAE including information about the event and its outcome, cigarette and SREC use history, concomitant medications, the participant's medical history and current conditions, and all relevant laboratory data. An initial notification with all related study forms shall be made to the DSMB within 72 hours of the detection of an unexpected SAE. Any additional information about the case that may be obtained after the initial notification shall be communicated to the DSMB in a timely manner. The DSMB may require a conference call to review all the relevant information and the study safety monitor's determination of whether there was any possible relevance to the study and discuss and approve a Corrective and Preventive Action Plan, if warranted.

